5.1.2. Unscheduled Visits

All attempts should be made to keep patients on the study schedule. Unscheduled visits may be necessary to repeat testing following abnormal laboratory results, for follow-up of AEs, or for any other reason, as warranted.

5.1.3. Adverse Event Information Collection

The investigator (or designee) will record all AEs that occur during the study. The definition of an AE and SAE, and information on the determination of severity and relationship to treatment are provided in [Section 7](#).

5.3. Rescue Criteria

Patients will be rescued at any time at the investigator's discretion by removal of DEXTENZA® by manual expression or flushing down the nasolacrimal duct.

6. SAFETY DEFINITIONS, REPORTING, AND MONITORING

6.1. Definitions

6.1.1. Adverse Event

An AE is any untoward medical occurrence in a patient administered a study drug which may or may not have a causal relationship with the study drug. Therefore, an AE is any unfavorable and unintended sign (including abnormal laboratory finding), symptom, or disease which is temporally associated with the use of a study drug, whether or not considered related to the study drug.

An AE also includes any worsening (i.e. any clinically significant change in frequency and/or intensity) of a pre-existing condition that is temporally associated with the use of the study drug.

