Intracanalicular Dexamethasone used in conjunction with Restasis (cyclosporine ophthalmic emulsion) for the treatment of signs and symptoms of dry eye disease as compared to Restasis with Lotemax (loteprednol etabonate ophthalmic suspension 0.5%) and Restasis monotherapy.

[name] STUDY

Compound:

DEXTENZA® (dexamethasone ophthalmic insert) 0.4 mg for intracanalicular use

Study Name:

[name] STUDY

Protocol Number:

TC-2020-DexRes

Clinical Phase:

Open label prospective

Date of Issue:

01/11/2021

Primary Investigator:

[name]

Site Name & Location:

Cleveland Eye Clinic
[name],
[name]

[name] STUDY V2

CLINICAL STUDY PROTOCOL SYNOPSIS

TITLE	Intracanalicular Dexamethasone used in conjunction with Restasis (cyclosporine ophthalmic emulsion) for the treatment of signs and symptoms of dry eye disease as compared to Restasis with Lotemax (loteprednol etabonate ophthalmic suspension 0.5%) and Restasis monotherapy.
SITE LOCATION(S)	Cleveland Eye Clinic [name]
PRINCIPAL INVESTIGATOR	[name]
OBJECTIVE(S)	To evaluate the benefit of treatment with a physician administered intracanalicular dexamethasone insert in patients with dry eye who are beginning treatment with Restasis (cyclosporine ophthalmic emulsion) to reduce the signs and symptoms of dry eye disease.
STUDY DESIGN	Prospective Open-label Interventional Study
STUDY DURATION	6 months including screening and enrollment
ESTIMATED STUDY COMPLETION DATE	3 months after date of insertion
POPULATION	
Sample Size:	30 patients (60 eyes)
Target Population:	Patients with dry eye who are about to begin treatment with Restasis bilaterally to reduce the signs and symptoms of dry eye disease and who have not been on topical immunomodulation for a minimum of 3 months prior to the start of the study.
TREATMENT(S)	

[name] STUDY V2

Study Drug	Sustained Release Dexamethasone, 0.4 mg
Dose/Route/Schedule:	All patients will be prescribed Restasis BID for both eyes who have not been on topical immunomodulation for a minimum of 3 months, and who would benefit from addition of topical pharmacotherapy (immunomodulation). There will be 3 groups. 10 patients will receive Restasis BID and Dextenza in both eyes, 10 patients will receive Restasis BID for 12 weeks and Lotemax BID for one month in both eyes and 10 patients will receive Restasis BID monotherapy.

Screening/ Prescription

- 1-week
- 2-week
- 1 month
- 2 month
- 3 month

ENDPOINT(s)

PRIMARY:

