5. STUDY SCHEDULE OF EVENTS AND VISIT DESCRIPTIONS

5.1. Schedule of Events

Study assessments and procedures are presented by visit in [Table 1](#).

[name] STUDY V2

Table 1 Schedule of Events

Study Procedure	Screening/ Prescription	Week 1	Week 2	Week 4	Week 8	Week 12
Visit	VISIT 1	VISIT 2	VISIT 3	VISIT 4	VISIT 5	VISIT 6
Windows for Visits	(Day -30 to -1)	+/- 1 day	+/- 3 days	+/- 3 days	+/- 3 days	+/- 3 days
vInclusion/Exclusion	x					
Informed Consent	x					
Demographics	x					
Medical History and Concurrent Illnesses	x					
Concomitant Medications	x	x	x	x	x	x
UCVA Testing	x	x	x	x	x	x
MR/BCVA (ETDRS at 4m)	x	x	x	x	x	x
Schirmer's Test	x	x	x	x	x	x
Ophthalmic Examination (w/ or w/o dilation)	x	x	x	x	x	x
Meibomian gland assessment (expressibility and quality)	x	x	x	x	x	x
MMP9 with Inflamma Dry	x	x	x	x	x	x
Tear Osmolarity with Tear Lab	x	x	x	x	x	x
Conjunctival Injection Scale 0-4	x	x	x	x	x	x
NaFl Staining	x	x	x	x	x	x
TBUT	x	x	x	x	x	x
Lissamine Green	x	x	x	x	x	x

[name] STUDY V2

Intraocular Pressure	x	x	x	x	x	x
Restasis/Lotemax prescription	x					
Intracanalicular dexamethasone insert	x					
Physician ease of insertion questionnaire	x					
Insert Visualization	x	x	x	x	x	x
Subject reported AEs after insertion	x	x	x	x	x	x
DEQ-5	x	x	x	x	x	x

Study Visit Descriptions

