5.1.1. Study Procedures

Screening/Prescription

After the patient has provided informed consent, the following information will be collected:

- Inclusion/exclusion
- Demographics
- Medical history and concurrent illnesses
- Concomitant medications
- UCVA and MR/BCVA as measured by ETDRS chart at 4m
- Ophthalmic Examination with dilation
- Intraocular pressure
- Meibomian gland assessment (expressibility and quality)
- DED Assessment
 - Schirmer's
 - MMP9
 - Osmolarity
 - Conjunctival injection
 - TBUT
 - Ocular surface staining (sodium fluorescein and lissamine green)
- Subject reported AE's
- Restasis BID OU prescription
- Lotemax BID OU for 1 month prescription
- DEXTENZA® insertion in one eye

- Insert Visualization
- Physician ease of insertion questionnaire
- DEQ-5 

Week 1, Week 2, Week 4 and Week 8

- UCVA and MR/BCVA as measured by ETDRS chart at 4m
- Concomitant Medications
- Ophthalmic Examination without dilation and with IOP
- Insert visualization
- Meibomian gland assessment (expressibility and quality)
- DED Assessment
 - Schirmer's
 - MMP9
 - Osmolarity
 - Conjunctival injection
 - TBUT
 - Ocular surface staining (sodium fluorescein and lissamine green)
- Subject reported AE's
- DEQ-5 

Week 12

- UCVA and MR/BCVA as measured by ETDRS chart at 4m
- Concomitant Medications
- Ophthalmic Examination without dilation and with IOP
- Insert visualization
- Meibomian gland assessment (expressibility and quality)
- DED Assessment
 - Schirmer's
 - MMP9
 - Osmolarity
 - Conjunctival injection
 - TBUT
 - Ocular surface staining (sodium fluorescein and lissamine green)
- Subject reported AE's
- DEQ-5 

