6.2. Recording and Reporting Adverse Events

All AEs and SAEs will be recorded only if they are medically relevant.

All SAEs, regardless of assessment of causal relationship to study insert will be reported to Ocular Therapeutix.

To report an SAE, Ocular Therapeutix will be contacted at the following:

[contact]

SAE [contact]

The investigator will promptly report to the IRB all unanticipated problems involving risks to patients. This includes death from any cause and all SAEs related to the use of the study insert. All SAEs will be reported to the IRB, regardless of assessed causality.

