## CONCLUSION

The challenges of topical medication use are widespread and well recognized across ophthalmology. The safety profile reported in this study, albeit a small sample size, indicates the dexamethasone intracanalicular insert is a safe alternative option to topical steroids to augment the anti-inflammatory properties of topical cyclosporine 0.05%. Further study is necessary but use of the dexamethasone insert may provide a means to optimize medication delivery without compromising safety or efficacy in the treatment of dry eye disease.

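### The AE wording conflicts on whether the control arms are covered, and no control-arm AE results are reported behind the safety comparison with topical steroids

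*Protocol*

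**What the plan says.** Some wording points to the insert. Under the study-drug label the Protocol synopsis names one product, "Sustained Release Dexamethasone, 0.4 mg". Section 6.1.1 opens "An AE is any untoward medical occurrence in a patient administered a study drug", and Section 6 does not say which products that term covers. The Table 1 row is "Subject reported AEs after insertion", marked at all six visits. In Section 6.2 the only product named when relationship is mentioned is the insert: SAEs, "regardless of assessment of causal relationship to study insert will be reported to Ocular Therapeutix".

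Other wording has no such limit. Section 5.1.3 says "The investigator (or designee) will record all AEs that occur during the study". The visit lists in 5.1.1 carry "Subject reported AE's" at screening and at every follow-up visit. The SAP (Main Outcome Measures) says that subject-reported AEs were recorded at each visit.

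Two further passages bear on the point. Section 6.2 restricts the recording of AEs and SAEs to those that are medically relevant. Section 5.1.3 says that "information on the determination of severity and relationship to treatment are provided in" Section 7, but that section holds only demographic and baseline variables.

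The SAP Results give IOP findings for all three groups and an AE statement tied to implantation of the insert. The SAP Conclusion calls the insert "a safe alternative option to topical steroids".

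**The concern.** The SAP Conclusion compares the insert with topical steroids on safety, so the reader needs to know what happened in the arms without an insert. A site following 6.1.1 and Table 1 literally could record less for a loteprednol or monotherapy patient than for an insert patient. A site following 5.1.1 and 5.1.3 would record the same for all. In an open-label study, an undefined medical-relevance filter leaves further room for judgement by someone who knows the arm.

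The events most likely to matter are mild. The SAP Introduction names burning, stinging and conjunctival hyperemia on instillation of cyclosporine, which all 30 patients receive, and says short-term steroids have been used to mitigate them. SAE reporting would not be expected to pick these up. Without relationship criteria, and with the insert the only product named, the Protocol does not tell the site how to attribute such an event to Restasis or Lotemax.

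**Working it through.** **1. How many patients are affected.** Planned (Protocol 3.1): 10 Lotemax + 10 monotherapy = 20 of 30. Enrolled (SAP Results): 11 + 9 = 20 of 30.

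**2. The passages side by side.**
- *Definition.* 6.1.1 depends on what a study drug is. The synopsis label gives insert only. The dosing entry directly below that label describes all three regimens, so the synopsis itself can be read either way.
- *Collection.* Table 1 conditions the row on insertion. 5.1.1, 5.1.3 and the SAP do not.
- *Filter.* 5.1.3 requires every AE to be recorded. 6.2 requires only the medically relevant ones and gives no criterion. This conflict affects every arm.
- *Relationship and severity.* 5.1.3 speaks of relationship to treatment in general and refers to Section 7, which has no criteria. Section 6 holds the AE and SAE definitions but no severity or relationship criteria either. Pointing 5.1.3 to Section 6 would therefore not close the gap.
- *SAEs.* The definition in 6.1.2 has no insert condition, and 6.2 sends all SAEs to the IRB whatever their causality.

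**3. What is reported by arm.**
- *IOP.* Described as stable in all three groups, with no rise of more than 10 mmHg above baseline in any. No follow-up values are tabulated. The baseline IOP row in SAP Table 1 (6.6 ± 2.2, 5.4 ± 1.5, 5.7 ± 3.3) is identical to the baseline tear break-up time row in SAP Table 2, so one of them needs correcting.
- *AEs.* Insert-related statement only, with no count for loteprednol or monotherapy. The Discussion's statement that there were no AEs refers to the insert combination.
- *Conjunctival injection.* Graded 0 to 4 at every visit with no arm restriction (Protocol Table 1 and appendix II), but absent from the SAP outcomes and tables.

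**4. Scale of what an AE table could show.** The documents give no safety calculation, so this is for orientation. With zero events in n patients, the one-sided 95% upper limit on the true rate is 1 − 0.05^(1/n), and the two-sided limit is 1 − 0.025^(1/n).
- n = 10 (insert): 25.9% and 30.8%
- n = 11 (loteprednol): 23.8% and 28.5%
- n = 9 (monotherapy): 28.3% and 33.6%
- n = 20 (both controls): 13.9% and 16.8%

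An AE with a true rate of 10% would be missed altogether in 10 patients with probability 0.9^10 = 0.35. By Fisher's exact test, the smallest excess over zero control events that reaches two-sided p < 0.05 is 3/10 against 0/20 (p = 0.030), or 4/10 against 0/11 for loteprednol alone (p = 0.035). A table by arm would therefore be descriptive, and could not by itself establish equal safety.

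**The case against.** A reader might infer that 20 of 30 patients lie outside AE collection, that ascertainment did differ by arm, and that the safety conclusion has no comparator at all. The documents do not support this.
- 6.1.1 does not mention the insert, and the insert-only reading rests on one synopsis label.
- Protocol 5.1.1 and 5.1.3 and the SAP all describe unrestricted collection.
- Insertion serves loosely as time zero throughout the Protocol. Section 3.1 dates each patient's follow-up from it, although 20 patients have no insert, and Table 1 has no arm split in any row. The AE row may be no more than careless drafting.
- The insert wording in 6.2 concerns SAE reporting, partly to the insert's supplier, and does not depend on causality. Nothing forbids attributing an event to Restasis or Lotemax, and the AE form is not among the documents.
- IOP, which the SAP names as a steroid risk, is reported in all three arms.

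All of this stands, and it reduces the point to inconsistent wording plus a reporting gap. It does not supply the missing control-arm AE results, the missing criteria or a resolution of the filter. Nor does it explain why the Results, having said that all subject-reported AEs were recorded, give them only for the insert.

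**Conclusion.** The point holds as an internal inconsistency with a visible effect on reporting. The AE definition and the Table 1 row can be read as insert-only, against unrestricted wording elsewhere. The medical-relevance filter conflicts with recording all AEs. Severity and relationship criteria are absent for every arm. No AE count is given for the 20 control patients, so apart from IOP the comparison with topical steroids has no reported comparator AE data. Differential ascertainment is a possibility, not a finding.

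This rests on two assumptions: that the SAP text shows all the AE results there are, and that the visit forms hold AE entries for every arm, as the SAP implies. If the second is wrong, the comparison cannot be rescued by tabulation. The point should be acted on because it changes what the trial can say about safety.

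**What to change.** **Protocol**
- Define study treatment in 6.1.1 and 6.2 as every product given in the patient's arm.
- Remove the insertion condition from the Table 1 AE row and count AEs in every arm from first study treatment.
- Reconcile the medical-relevance filter in 6.2 with the all-AE rule in 5.1.3. Otherwise a table by arm could still be incomplete.
- Correct the Section 7 reference, add severity and relationship criteria where it points, and record relationship separately for each product received.

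**SAP**
- Tabulate patients with any AE by arm from the existing visit forms, descriptively and per patient.
- Report the conjunctival injection grade by arm, since it is already scheduled.
- Check the baseline IOP row before relying on IOP as the comparative safety measure.
- If control-arm AEs were not collected on the same basis, limit the safety conclusion to the insert arm and IOP, and drop the comparison with topical steroids.

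The cost is some wording, one form field and one extra AE table, plus a summary of injection grades already collected. No visits are added. The safety statement may become less favourable.

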6.1.2. Serious Adverse Event

A SAE is any untoward medical occurrence that at any dose:

- Results in **death** – includes all deaths, even those that appear to be completely unrelated to study drug (e.g. a car accident in which a patient is a passenger).
- Is **life-threatening** – in the view of the investigator, the patient is at immediate risk of death at the time of the event. This does not include an AE that had it occurred in a more severe form, might have caused death.
- Requires in-patient **hospitalization** or prolongation of existing hospitalization. In-patient hospitalization is defined as admission to a hospital or an emergency room for longer than 24 hours. Prolongation of existing hospitalization is defined as a hospital stay that is longer than was originally anticipated for the event, or is prolonged due to the development of a new AE as determined by the investigator or treating physician.
- Results in persistent or significant **disability/incapacity** (substantial disruption of one's ability to conduct normal life functions).
- Is a **congenital anomaly/birth defect**
- Is an **important medical event** – Important medical events may not be immediately life-threatening or result in death or hospitalization, but may jeopardize the patient or may require intervention to prevent 1 of the

other serious outcomes listed above (e.g., intensive treatment in an emergency room or at home for allergic bronchospasm; blood dyscrasias or convulsions that do not result in hospitalization; or development of drug dependency or drug abuse). Any malignancy (other than basal cell skin cancers) would be considered a medically important event.

6.2. Recording and Reporting Adverse Events

All AEs and SAEs will be recorded only if they are medically relevant.

All SAEs, regardless of assessment of causal relationship to study insert will be reported to Ocular Therapeutix.

To report an SAE, Ocular Therapeutix will be contacted at the following:

[contact]

SAE [contact]

The investigator will promptly report to the IRB all unanticipated problems involving risks to patients. This includes death from any cause and all SAEs related to the use of the study insert. All SAEs will be reported to the IRB, regardless of assessed causality.

7. STUDY VARIABLES

7.1. Demographic and Baseline Characteristics

Baseline characteristics will include standard demography (e.g. age, race, weight, height, etc.), disease characteristics including medical history, and medication history for each patient.

8. ETHICAL AND REGULATORY CONSIDERATIONS

8.1. Good Clinical Practice Statement

It is the responsibility of the investigator(s) to ensure that this clinical study will be conducted in accordance with the ethical principles that have their origin in the Declaration of Helsinki, and that are consistent with the ICH guidelines for Good Clinical Practice (GCP) and applicable regulatory requirements.

8.2. Informed Consent

The principles of informed consent are described in ICH Guidelines for GCP.

Ocular Therapeutix will have the right to review and comment on the informed consent form.

It is the responsibility of the investigator or designee (if acceptable by local regulations) to obtain written informed consent from each patient prior to his/her participation in the study and after the aims, methods, objectives, and

potential hazards of the study have been explained to the patient in language that he/she can understand. The ICF will be signed and dated by the patient and by the investigator or authorized designee who reviewed the ICF with the patient.

Patients who can write but cannot read will have the ICF read to them before signing and dating the ICF.

Patients who can understand but who can neither write nor read will have the ICF read to them in presence of an impartial witness, who will sign and date the ICF to confirm that informed consent was given.

The original ICF will be retained by the investigator as part of the patient's study record, and a copy of the signed ICF will be given to the patient.

If new safety information results in significant changes in the risk/benefit assessment, the ICF will be reviewed and updated appropriately. All study patients will be informed of the new information and provide their written consent if they wish to continue in the study. The original signed revised ICF will be maintained in the patient's study record and a copy will be given to the patient.

8.3. Patient Confidentiality and Data Protection

The investigator will take all appropriate measures to ensure that the anonymity of each study patient will be maintained.

The patient's and investigator's personal data will be treated in compliance with all applicable laws and regulations.

8.4. Institutional Review Board

An appropriately constituted IRB, as described in ICH Guidelines for GCP, will review and approve:

- The protocol, ICF, and any other materials to be provided to the patients (e.g. advertising) before any patient may be enrolled in the study
- Any amendment or modification to the study protocol or ICF before implementation, unless the change is necessary to eliminate an immediate hazard to the patients, in which case the IRB will be informed as soon as possible

Ongoing studies will be reviewed by the IRB/EC on an annual basis or at intervals appropriate to the degree of risk.

In addition, the IRB will be informed of any event likely to affect the safety of patients or the continued conduct of the clinical study.

[name] STUDY V2

A copy of the IRB approval letter will be sent to Ocular Therapeutix prior to shipment of drug insert supplies to the investigator. The approval letter will include the study title, the documents reviewed, and the date of the review.

Records of the IRB review and approval of all study documents (including approval of ongoing studies) will be kept on file by the investigator.

REFERENCES

2. TFOS International Dry Eye WorkShop (DEWS II). *Ocular Surf.* 2017;15(6):269-650.
3. Schultz C. Safety and Efficacy of Cyclosporine in the Treatment of Chronic Dry Eye. *Ophthalmol Eye Dis.* 2014; 6: 37–42. Published online 2014 Jun 24.
5. DEXTENZA (dexamethasone insert) Prescribing Information, Ocular Therapeutix, Inc. 2019 <http://www.dextenza.com/wp-content/uploads/2019/06/NDA-208742-S001-Dextenza-labeling-19Jun19.pdf>
7. Walters TR, et al. Efficacy and Safety of Sustained Release Dexamethasone for the Treatment of Ocular Pain and Inflammation after Cataract Surgery: Results from Two Phase 3 Studies. *J Clin Exp Ophthalmol.* 2016; 7(4): 572.

APPENDICES

I. The investigator will use the NEI scale to grade the cornea using fluorescein and the conjunctiva using lissamine green at visits 1, 2, 3, 4, 5, 6.

II. The investigator will grade the level of ocular injection on a 0 to 4-point scale at visits 1, 2, 3, 4, 5, 6.

0 = None

1 = Mild – Slightly dilated blood vessels; color of vessels is typically pink; can be quadrantal

2 = Moderate – More apparent dilation of blood vessels; vessel color is more intense (redder); involves the majority of the vessel bed

3 = Severe – Numerous and obvious dilated blood vessels; in the absence of chemosis the color is deep red, may be less red or pink in presence of chemosis, is not quadrantic

4 = Extremely Severe – Large, numerous, dilated blood vessels characterized by unusually severe deep red color, regardless of grade of chemosis, which involves the entire vessel bed

III. The investigator will evaluate the expressibility and quality of the meibomian glands at visits 1, 2, 3, 4, 5, 6..

Grade scale for meibomian gland dysfunction		
Grade Scale	Percentage of blocked glands	Quality of meibomian secretion
Grade 1	40% - 50%	Clear to mild milky secretion
Grade 2	50% - 70%	Milky to pasty secretion
Grade 3	70% - 85%	Thick, pasty to very little secretion
Grade 4	85% - 90%	Very little to no secretion

IV. The investigator will use the InflammaDry to detect levels of MMP9 at visits 1, 2, 3, 4, 5, 6.

[figure not shown]

InflammaDry

[name] STUDY V1

V. The investigator will use Tear Lab to assess tear osmolarity at visits 1,2, 3, 4, 5, 6.

VI. The investigator will fill out the following questionnaire on the day of DEXTENZA® insertion (Screening visit):

Physician Ease of Insertion Questionnaire

The investigator will grade the level of ease of insertion of the intracanalicular insert on a 0 to 10-point scale.

The Investigator will record ease of insertion procedure on the appropriate Case Report Form.

0	1	2	3	4	5	6	7	8	9	10
---	---	---	---	---	---	---	---	---	---	----

Very Easy

Very Hard

VII. The investigator will have the patient complete the DEQ-5 questionnaire at visits 1,3,4,5,6,7.

DEQ-5

1. Questions about EYES DRYNESS:

a. During a typical day in the past month, how often did your eyes feel discomfort?

Never
 Rarely
 Sometimes
 Frequently
 Constantly

b. When your eyes feel discomfort, how intense was this feeling of discomfort at the end of the day, within two hours of going to bed?

Never have it Not at all intense Very intense

0
 1
 2
 3
 4
 5

